5.4 Patient Demographics and Frequency of Adverse Drug Reactions / Infections by Treatment

5.4.1 Patients demographics and Frequency of Adverse Drug Reactions / Infections by Treatment

(1) Patients to be tabulated and analyzed

Safety Analysis Set

(2) Details of tabulation and analysis

Each parameter will be categorized by the categories described below to tabulate the percent of patients with adverse drug reactions, etc.

The Fischer exact test will be used for parameters without rank data. The Mann-Whitney U test will be used for parameters with rank data. (The tests will be used for parameters with asterisk [*].)

Total and mild type 2 diabetes mellitus patients will be tabulated.

Parameter	Category
Sex*	Male, Female
Age*	< 65 years, ≥65 years
	< 75 years, ≥75 years
Severity of renal impairment*	Normal + Mild, Moderate + Severe
Concurrent liver disorder*	No, Yes
Concurrent renal disorder*	No, Yes
Concurrent heart disease*	No, Yes
Details of concurrent heart disease	Cardiac failure, myocardial infarction, or angina pectoris

Parameter	Category
(overlapped)	
Concurrent cardiac failure*	No, Yes
Severity classification of cardiac failure (NYHA classification)*	Classes NYHA I, NYHA II, NYHA III, and NYHA IV
Concurrent stroke-related disease*	No, Yes
Mean daily dose of Nesina	> 25 mg, 25 to >12.5 mg, 12.5 to > 6.25 mg, or ≤6.25 mg
Administration of concomitant medication (diabetic drug)	No, Yes
Concomitant medications (diabetic drugs) (overlapped)	α-glucosidase inhibitors, thiazolidines, sulfonylureas, biguanides, rapid-acting insulin secretagogues, or insulin preparations
Administration of concomitant medication (protease drug)*	No, Yes
Administration of concomitant medication (combined with renal excretory drug)*	No, Yes

(3) Number of tables and figures

Table 5.4.1-1

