#### 10.4.2 Factors Probably Affecting Safety

For adverse drug reactions reported in the observation period, the frequency of patient demographics (e.g., age, sex), details of treatment (e.g., status of Nesina, and status of concomitant medications) will be stratified.

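### SAP 5.4.1 tests each factor for adverse drug reactions on its own, with no age adjustment and no ratio, difference or interval, so an age effect can appear under another factor's name

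*SAP*

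**What the plan says.** Protocol 10.4.2, on factors probably affecting safety, promises only stratified frequencies: "For adverse drug reactions reported in the observation period, the frequency of patient demographics" and of treatment details.

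SAP 5.4.1 carries this out. Each parameter is split into categories "to tabulate the percent of patients with adverse drug reactions, etc". The tests are then named: "The Fischer exact test will be used for parameters without rank data. The Mann-Whitney U test will be used for parameters with rank data". They apply to some rows only: "The tests will be used for parameters with asterisk".

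Eleven parameters are starred: sex, age, renal impairment severity, liver disorder, renal disorder, heart disease, cardiac failure, NYHA class, stroke-related disease, protease drug and renal excretory drug. Age is split twice, at 65 ("< 65 years, ≥65 years") and at 75, which makes twelve tests. The table is produced for the total and again for mild type 2 diabetes. SAP 1.4 sets the level at two-sided 5%.

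Age is one more row in the table and is never used to stratify or adjust "Severity of renal impairment", "Concurrent heart disease" or "Concurrent stroke-related disease". SAP versions 1.0 and 2.0 have the same wording.

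**The concern.** In a single-arm survey, a one-way comparison of ADR percentages cannot tell a renal effect from an age effect if older patients have both more renal impairment and more ADRs. The same reasoning applies to every other starred factor that goes with age. A significant p-value could then be credited to the wrong factor, or to several factors for one underlying reason.

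A second gap needs no confounding. In a small category, a non-significant p-value without an interval does not show how large an effect the data still allow.

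This matters because safety is half of the objective (Protocol 2.0), SAP 5.4.1 is the only place where factors for ADRs are tested, and renal impairment has its own protocol section (10.6).

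**Working it through.** **Does another section fill the gap?** SAP 5.5 to 5.19 break ADRs down by one factor at a time. Only 5.15 combines two, mean daily dose within moderate or higher renal impairment, and it does not involve age. Intervals are specified for mean changes in vital signs and laboratory values (5.20) and in efficacy measures (6.1, 6.3 to 6.5), never for an ADR comparison.

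**The plan's own size calculation.** Protocol 3.2 needs 600 patients to see an ADR of frequency 0.5% with 95% confidence. ln(0.05)/ln(0.995) = 597.6, so 598, or 3/0.005 = 600 by the rule of three. The figure reproduces, but it concerns seeing at least one event, not comparing factors. The planned total is 20,000 (Protocol 3.1).

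**Illustration for renal impairment.** All rates are assumptions, because the documents give no age split, prevalence or ADR rate. Half the patients are 65 or older. Within each age group, ADR risk is the same with and without moderate or severe renal impairment, so the true renal effect is nil. Let r be the prevalence of renal impairment and a the ADR risk, with subscripts o (65 or older) and y (younger).

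- Crude ADR risk, renal = (0.5·r_o·a_o + 0.5·r_y·a_y) / (0.5·r_o + 0.5·r_y); the non-renal risk uses 1−r in place of r.
- z = difference / √[p(1−p)(1/n₁ + 1/n₀)], where p is the overall ADR risk.
- Chance of p<0.05 = Φ(z−1.96) + Φ(−z−1.96).

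Worked row (r 20% vs 2%, a 4% vs 2%):

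- Renal: (0.0040 + 0.0002)/0.11 = 3.82%.
- Non-renal: (0.0160 + 0.0098)/0.89 = 2.90%.
- n₁ = 2,200, n₀ = 17,800, p = 0.03, so the standard error is 0.00386 and z = 0.00919/0.00386 = 2.38.
- Chance of a flag: Φ(0.42) = 66%.

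| Renal impairment, ≥65 vs <65 | ADR risk, ≥65 vs <65 | Crude ADR, renal vs not | Crude RR | Flagged at p<0.05 |
|---|---|---|---|---|
| 10% vs 3% | 2.5% vs 2% | 2.38% vs 2.24% | 1.06 | 6% |
| 10% vs 3% | 3% vs 2% | 2.77% vs 2.48% | 1.12 | 10% |
| 12% vs 2% | 3% vs 2% | 2.86% vs 2.47% | 1.16 | 14% |
| 20% vs 2% | 3% vs 2% | 2.91% vs 2.45% | 1.19 | 26% |
| 12% vs 2% | 4% vs 2% | 3.71% vs 2.95% | 1.26 | 37% |
| 20% vs 2% | 4% vs 2% | 3.82% vs 2.90% | 1.32 | 66% |
| 20% vs 2% | 6% vs 2% | 5.64% vs 3.80% | 1.48 | 99% |

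Fisher's exact test, which is the planned test, is slightly more conservative than this z approximation: about 64% instead of 66% in the worked row.

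**Does age stratification cure it?** A separate simulation used 600 surveys of 20,000 per scenario, renal impairment in 15% vs 3% or 20% vs 5% by age, and ADR risk in the young of 1%, 2% or 5%. Fisher flagged renal impairment in 4-6% of surveys with no age effect, 6-16% at an age risk ratio of 1.25, 12-35% at 1.5 and 21-80% at 2.0. The age-stratified Mantel-Haenszel test flagged 3-7% throughout, with average odds ratios of 0.97-1.00. The standard error of the log odds ratio was 0.08-0.26, so a usable interval is available.

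**The interval point.** Take a hypothetical small category with 6/100 ADRs against 597/19,900 elsewhere. Fisher's p is 0.13. The risk ratio is 6%/3% = 2.0. SE(log RR) = √(1/6 − 1/100 + 1/597 − 1/19,900) = 0.398, giving a 95% CI of about 0.9 to 4.4. The p-value alone hides that a fourfold risk is not excluded.

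**The case against.** The strongest reply is that this is a descriptive survey. Protocol 10.4.2 asks only for stratified frequencies, SAP 5.4.1 delivers them, and nothing in either document attaches a decision to p<0.05. That stands. A reader might infer that the table is meant to yield a list of established risk factors, but the documents do not say so.

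A reader might also infer that the plan gives no information on effect size. That goes too far: percentages by category are reported to two decimals (SAP 1.3), so a crude difference or ratio can be read off. What is missing is a specified contrast, its interval and any adjustment.

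It is equally tempting to say that the starred factors are strongly tied to age and that false flags are therefore likely. The documents give no correlations, prevalences or ADR rates. Under weak gradients the flag rate is about 6%, close to nominal, and the 66-99% results need a tenfold age gradient in renal impairment and at least a doubling of ADR risk with age. Only renal impairment was calculated. Nothing here measures the problem for heart disease or stroke. That readers would take a non-significant result as absence of risk is likewise conjecture.

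The reply does not remove the point. The plan chose a 5% level and chose which factors to test, so the p-values will be read as evidence on those factors. Adjustment has limits too: age- and sex-adjusted ratios do not account for Nesina dose or for unequal follow-up, since observation ends at discontinuation (Protocol 7.1).

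**Conclusion.** The concern holds as a risk of misinterpretation in a descriptive analysis; it is not an error in a primary result. SAP 5.4.1 compares factors one at a time by unadjusted p-values. If age is related both to a factor and to ADR risk, a factor with no effect of its own can be flagged. For renal impairment with 20,000 patients this would happen in about 6% of surveys under weak age gradients, 10-37% under moderate ones and 66-99% under strong ones, against about 5% after age stratification. These figures rest on assumed age split, prevalences and ADR rates, and on the planned number being reached. The absence of an interval stands without any of these assumptions.

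The calculation takes ADR in its ordinary sense. SAP 1.1 defines the term as events judged not related to Nesina, which appears inverted. That is a separate matter to settle, because it governs the outcome in this whole table.

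**What to change.** Add columns to Table 5.4.1-1 beside the crude percentages:

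- For each starred factor other than age and sex, report an odds ratio or risk ratio with 95% CI adjusted for age (<65, 65-74, ≥75, which combines the SAP's two cut-points) and sex. Use logistic regression or Mantel-Haenszel, with one factor per model. This keeps a result for every tested factor and avoids adjusting one condition for another that may follow from it.
- Report age and sex adjusted for each other.
- Keep the Fisher and Mann-Whitney p-values, labelled exploratory, and rest statements on factors affecting safety on the adjusted estimates and their intervals.
- State that the renal estimate is not adjusted for Nesina dose, which SAP 4.1 and 5.15 examine separately.

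The data are already collected (Protocol 9.1 to 9.3). The cost is one more set of columns. Sparse categories such as NYHA classes may give wide or inestimable intervals. Patients with a missing factor drop from that estimate, and their number should be shown.

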5.5 Occurrence of Adverse Drug Reactions / Infections by Age

(1) Patients to be tabulated and analyzed

Safety Analysis Set

(2) Details of tabulation and analysis

Age will be classified into < 65 years, ≥65 years and < 75 years, and ≥75 years for tabulation of type of adverse drug reactions, etc.

The method for tabulation of adverse drug reactions, etc. is same as that described in Section 5.1.

Total and mild type 2 diabetes mellitus patients will be tabulated.

(3) Number of tables and figures

Tables 5.5-1 to 5.5-2

5.6 Occurrence of Adverse Drug Reactions / Infections by Sex

(1) Patients to be tabulated and analyzed

Safety Analysis Set

(2) Details of tabulation and analysis

Sex will be classified into male or female for tabulation of type of adverse drug reactions, etc.

The method for tabulation of adverse drug reactions, etc. is same as that described in Section 5.1.

Total and mild type 2 diabetes mellitus patients will be tabulated.

(3) Number of tables and figures

Table 5.6-1

5.7 Occurrence of Adverse Drug Reactions / Infections by Liver Disorder

(1) Patients to be tabulated and analyzed

Safety Analysis Set

(2) Details of tabulation and analysis

Concurrent liver disorder will be classified into yes or no for tabulation of type of adverse drug reactions, etc.

The method for tabulation of adverse drug reactions, etc. is same as that described in Section 5.1.

Total and mild type 2 diabetes mellitus patients will be tabulated.

(3) Number of tables and figures

Table 5.7-1

5.8 Occurrence of Adverse Drug Reactions / Infections by Presence of Concurrent Renal Disorder

(1) Patients to be tabulated and analyzed

Safety Analysis Set

(2) Details of tabulation and analysis

Concurrent renal disorder will be classified into yes or no for tabulation of type of adverse drug reactions, etc.

The method for tabulation of adverse drug reactions, etc. is same as that described in Section 5.1.

Total and mild type 2 diabetes mellitus patients will be tabulated.

- (3) Number of tables and figures

Table 5.8-1

5.9 Occurrence of Adverse Drug Reactions / Infections by Severity of Renal Impairment

- (1) Patients to be tabulated and analyzed

Safety Analysis Set

- (2) Details of tabulation and analysis

Severity of renal impairment will be classified into normal + mild or moderate + severe for tabulation of type of adverse drug reactions, etc.

The method for tabulation of adverse drug reactions, etc. is same as that described in Section 5.1.

Total and mild type 2 diabetes mellitus patients will be tabulated.

- (3) Number of tables and figures

Table 5.9-1

5.10 Occurrence of Adverse Drug Reactions / Infections by Presence of Concurrent Heart Disease

- (1) Patients to be tabulated and analyzed

Safety Analysis Set

- (2) Details of tabulation and analysis

Concurrent heart disease will be classified into yes or no for tabulation of type of adverse drug reactions, etc.

The method for tabulation of adverse drug reactions, etc. is same as that described in Section 5.1.

Total and mild type 2 diabetes mellitus patients will be tabulated.

- (3) Number of tables and figures

Table 5.10-1

5.11 Occurrence of Adverse Drug Reactions / Infections by Presence of Concurrent Heart Failure

- (1) Patients to be tabulated and analyzed

Safety Analysis Set

- (2) Details of tabulation and analysis

Concurrent heart failure will be classified into yes or no for tabulation of type of adverse drug reactions, etc.

The method for tabulation of adverse drug reactions, etc. is same as that described in Section 5.1.

Total and mild type 2 diabetes mellitus patients will be tabulated.

- (3) Number of tables and figures

Table 5.11-1

5.12 Occurrence of Adverse Drug Reactions / Infections by Severity of Heart Failure

- (1) Patients to be tabulated and analyzed

Safety Analysis Set

- (2) Details of tabulation and analysis

Severity of heart failure will be classified into Class NYHA I, NYHA II, NYHA III, or NYHA IV for tabulation of type of adverse drug reactions, etc.

The method for tabulation of adverse drug reactions, etc. is same as that described in Section 5.1.

Total and mild type 2 diabetes mellitus patients will be tabulated.

- (3) Number of tables and figures

Table 5.12-1

5.13 Occurrence of Adverse Drug Reactions / Infections by Presence of Concurrent Stroke-related Disease

- (1) Patients to be tabulated and analyzed

Safety Analysis Set

- (2) Details of tabulation and analysis

Concurrent stroke-related disease will be classified into yes or no for tabulation of type of adverse drug reactions, etc.

The method for tabulation of adverse drug reactions, etc. is same as that described in Section 5.1.

Total and mild type 2 diabetes mellitus patients will be tabulated.

- (3) Number of tables and figures

Table 5.13-1

5.14 Occurrence of Adverse Drug Reactions / Infections by Mean Daily Dose of Nesina

- (1) Patients to be tabulated and analyzed

Safety Analysis Set

- (2) Details of tabulation and analysis

The mean daily dose of Nesina will be classified into > 25 mg, 25 to > 12.5 mg, 12.5 to > 6.25 mg, or ≤6.25 mg for tabulation of type of adverse drug reactions, etc.

The method for tabulation of adverse drug reactions, etc. is same as that described in Section 5.1.

Total and mild type 2 diabetes mellitus patients will be tabulated.

- (3) Number of tables and figures

Table 5.14-1

5.15 Occurrence of Adverse Drug Reactions / Infections by Mean Daily Dose of Nesina in Patients with Special Demographics (Patients with Moderate or Higher Renal Impairment)

(1) Patients to be tabulated and analyzed

Patients with moderate or higher renal impairment in the Safety Analysis Set

(2) Details of tabulation and analysis

The mean daily dose of Nesina will be classified into > 25 mg, 25 to > 12.5 mg, 12.5 to > 6.25 mg, or ≤6.25 mg for tabulation of type of adverse drug reactions, etc.

The method for tabulation of adverse drug reactions, etc. is same as that described in Section 5.1.

Total and mild type 2 diabetes mellitus patients will be tabulated.

(3) Number of tables and figures

Table 5.15-1

5.16 Occurrence of Adverse Drug Reactions / Infections by Administration of Concomitant Medication (Diabetic Drug)

(1) Patients to be tabulated and analyzed

Safety Analysis Set

(2) Details of tabulation and analysis

Administration of concomitant medication (diabetic drug) will be classified into yes or no for tabulation of type of adverse drug reactions, etc.

The method for tabulation of adverse drug reactions, etc. is same as that described in Section 5.1.

Total and mild type 2 diabetes mellitus patients will be tabulated.

(3) Number of tables and figures

Table 5.16-1

5.17 Occurrence of Adverse Drug Reactions / Infections by Concomitant Medication (Diabetic Drug)

(1) Patients to be tabulated and analyzed

Safety Analysis Set

(2) Details of tabulation and analysis

Concomitant medications (diabetic drugs) will be classified into the following drugs: α -glucosidase inhibitors, thiazolidines, sulfonylureas, biguanides, rapid-acting insulin secretagogues, or insulin preparations, for tabulation of type of adverse drug reactions, etc.

The method for tabulation of adverse drug reactions, etc. is same as that described in Section 5.1.

Total and mild type 2 diabetes mellitus patients will be tabulated.

(3) Number of tables and figures

Table 5.17-1

5.18 Occurrence of Adverse Drug Reactions / Infections by Presence of Concomitant Protease Inhibitors

- (1) Patients to be tabulated and analyzed

Safety Analysis Set

- (2) Details of tabulation and analysis

Concomitant protease inhibitor will be classified into yes or no for tabulation of type of adverse drug reactions, etc.

The method for tabulation of adverse drug reactions, etc. is same as that described in Section 5.1.

Total and mild type 2 diabetes mellitus patients will be tabulated.

- (3) Number of tables and figures

Table 5.18-1

5.19 Occurrence of Adverse Drug Reactions / Infections by Presence of Concomitant Renal Excretory

Drug

- (1) Patients to be tabulated and analyzed

Safety Analysis Set

- (2) Details of tabulation and analysis

Concomitant renal excretory drug be classified into yes or no for tabulation of type of adverse drug reactions, etc.

The method for tabulation of adverse drug reactions, etc. is same as that described in Section 5.1.

Total and mild type 2 diabetes mellitus patients will be tabulated.

- (3) Number of tables and figures

Table 5.19-1

5.20 Change in Laboratory/Measured Data

5.20.1 Vital Signs

- (1) Patients to be tabulated and analyzed

Safety Analysis Set

- (2) Details of tabulation and analysis

For blood pressure (systolic/diastolic) and weight, summary statistics will be calculated at each testing time point (start of Nesina treatment, 3 months, 6 months, 12 months, 18 months, 24 months, 30 months, and 36 months after Nesina treatment and last evaluation). For changes from the start of Nesina treatment, summary statistics and the mean 95% confidence intervals will be calculated.

Measured values (mean and standard deviation) of blood pressure (systolic/diastolic) and weight will be plotted. For the changes, the mean changes will be created using a bar graph.

Total and mild type 2 diabetes mellitus patients will be tabulated.

(3) Number of tables and figures

Table 5.20.1-1 and Figures 5.20.1-1 to 5.20.1-6

5.20.2 Laboratory Values

(1) Patients to be tabulated and analyzed

Safety Analysis Set

(2) Details of tabulation and analysis

For laboratory values of fasting triglyceride, total cholesterol, HDL-cholesterol, LDL-cholesterol, and non-HDL cholesterol, summary statistics will be calculated at each testing time point (start of Nesina treatment, 3 months, 6 months, 12 months, 18 months, 24 months, 30 months, and 36 months after Nesina treatment and last evaluation). For changes from the start of Nesina treatment, summary statistics and the mean 95% confidence intervals will be calculated.

The individual laboratory values described above (mean and standard deviation) will be plotted.

For the changes, the mean changes will be created using a bar graph.

Total and mild type 2 diabetes mellitus patients will be tabulated.

(3) Number of tables and figures

Table 5.20.2-1 and Figures 5.20.2-1 to 5.20.2-10

6.0 Efficacy Tabulation and Analysis

6.1 Changes in HbA1c

(1) Patients to be tabulated and analyzed

Efficacy Analysis Set

(2) Details of tabulation and analysis

For HbA1c (NGSP values), summary statistics will be calculated at each testing time point (start of Nesina treatment, 3 months, 6 months, 12 months, 18 months, 24 months, 30 months, and 36 months after Nesina treatment and last evaluation). For changes, summary statistics and the mean 95% confidence intervals will be calculated and the paired t-test will be performed.

Measured values of HbA1c (NGSP values) will be plotted and for the changes a bar graph will be created excluding the unknown category at each testing time point (start of Nesina treatment, 3 months, 6 months, 12 months, 18 months, 24 months, 30 months, and 36 months after Nesina treatment and last evaluation).

(3) Number of tables and figures

Table 6.1-1 and Figure 6.1-1

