### 3.0 Number of Planned Patients for Surveillance and the Rationales

#### 3.1 Number of Planned Patients for Surveillance

20000 patients

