## 6.0 Number of To-be Survey Sites by Department

Internal medicine or other department: Approximately 1000 sites

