1.0 Definition of Terms and Handling of Laboratory/Measured Data

1.1 Definitions

Term	Definition
Nesina	Nesina tablet(s) is abbreviated as Nesina in this statistical analysis plan.
SOC	System Organ Class of MedDRA/J MedDRA/J version 20.1 is used for this document.
HLGT	High level group term of MedDRA/J
PT	Preferred term of MedDRA/J
LLT	Lowest level term of MedDRA/J
Registered patients	Patients whose registration was approved
Survey sheet (electronic) collected patients	Patients whose survey sheets were sent via CCI [REDACTED]
Survey sheet (electronic) uncollected patients	Of the registered patients, patients whose survey sheets (electronic) were uncollected.
Safety Analysis Set	Of the survey sheet (electronic) collected patients, patients who were evaluated for safety analysis. For tabulation, the description of “total” means the Safety Analysis Set.
Not Safety Analysis Set	Of the survey sheet (electronic) collected patients, patients who were excluded from safety analysis
Efficacy Analysis Set	Of the Safety Analysis Set, patients who were evaluated for efficacy analysis
Not Efficacy Analysis Set	Of the Safety Analysis Set, patients who were excluded from the efficacy analysis
First date of Nesina treatment	Of the start dates of the Nesina treatment period in patients, the earliest date is defined as the first date of Nesina treatment.
Last date of Nesina treatment	Of the last dates of the Nesina treatment period in patients, the latest date is defined as the last date of Nesina treatment. If Nesina treatment is continued and the year, month, and date of the continued treatment period are specified, the year, month, and date of the continued treatment period are defined as the last date of Nesina treatment. If the data for the year, month, and date of the continued treatment period are missing, the following date is defined as the last date of Nesina treatment. (1) First date of Nesina treatment + 3 years (same month and date), if Nesina treatment is continued based on the survey sheet (electronic) after 36 months of treatment* (2) For other than the above, the first date of Nesina treatment + 1 year (same month and date), if Nesina treatment is continued based on the survey sheet (electronic) after 12 months of treatment**

Term	Definition

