1.4 Level of Significance and Confidence Coefficient

Two-sided 5%, two-sided 95%.

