2.0 Disposition of Patients (Patient Diagram)

(1) Patients to be tabulated and analyzed

Registered patients

(2) Details of tabulation and analysis

The following will be tabulated: the number of registered patients, number of medical site at which patients is registered, number of patients whose survey sheets (electronic) are collected, number of patients whose survey sheets (electronic) are not collected, number of patients in the Safety Analysis Set, number of patients in the Not Safety Analysis Set, number of patients in the Efficacy Analysis Set, and number of patients in the Not Efficacy Analysis Set.

For the number of medical sites at which patients are registered, do not duplicate the same medical site with different departments.

For patients whose survey sheets (electronic) are not collected, tabulate the number of patients for each reason for not collected survey sheets.

For the Not Safety Analysis Set and Not Efficacy Analysis Set, the number of patients will be tabulated for each reason for exclusion to create the list.

The following is the handling of the decision whether patients who meet the following criteria should be evaluated:

Criterion	Safety evaluation	Efficacy evaluation
Pre-agreement administration [found after administration]	×	×
Registration 15 days after the start of Nesina treatment [found after registration]	×	×
Nesina taking not confirmed [after the end of patient registration period]	×	×
No data for post-administration of Nesina	×	×
Data reliability was not confirmed	×	×
Other than patients with mild type 2 diabetes mellitus	○	×

○ Included, × Excluded or not evaluated

(3) Number of tables and figures

Figure 2.0-1 and Table 2.0-1

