6.4 Changes in HbA1c, etc. by Factor Probably Affecting Efficacy

(1) Patients to be tabulated and analyzed

Efficacy Analysis Set

(2) Details of tabulation and analysis

For changes in HbA1c (NGSP values), summary statistics and the mean 95% confidence intervals will be calculated and the paired t-test will be performed at each testing time point (start of Nesina treatment, 3 months, 6 months, 12 months, 24 months, and 36 months after Nesina treatment and last evaluation).

The Glycemic control achievement rate for HbA1c ($< 7.0\%$, $\geq 7.0\%$ / $< 6.0\%$, $\geq 6.0\%$) at each testing time point (start of Nesina treatment, 3 months, 6 months, 12 months, 24 months, and 36 months after Nesina treatment and last evaluation) will be tabulated at the following parameters:

i Sex (Male, Female)

ii Age (< 65 years, ≥ 65 years)

iii Age (< 75 years, ≥ 75 years)

iv Concurrent renal disorder (No, Yes)

v HbA1c (NGSP value) at the start of Nesina treatment ($< 6.0\%$, 6.0% to $< 7.0\%$, 7.0% to $< 8.0\%$, $\geq 8.0\%$)

vi Mean daily dose of Nesina (> 25 mg, 25 to > 12.5 mg, 12.5 to > 6.25 mg, or 6.25 mg)

vii Concomitant diabetic drugs (α -glucosidase inhibitors, thiazolidines, sulfonylureas, biguanides, rapid-acting insulin secretagogues, or insulin preparations)

(3) Number of tables and figures

Tables 6.4-1 to 6.4-14

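### The mean-change intervals and paired t-tests make no allowance for clustering in about 1,000 sites; if the site ICC of the change is above 0, the stated 95% and 5% are not met

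*SAP*

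**What the plan says.** Protocol 3.1 plans "20000 patients", and Protocol 6.0 gives the number of sites: "Internal medicine or other department: Approximately 1000 sites". SAP 1.4 sets the significance level and confidence coefficient as "Two-sided 5%, two-sided 95" per cent.

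For HbA1c, SAP 6.1 says "For changes, summary statistics and the mean 95% confidence intervals will be calculated and the paired t-test will be performed", and 6.3 does the same for fasting glucose and fasting insulin. The stratified HbA1c tables, SAP "6.4 Changes in HbA1c, etc. by Factor Probably Affecting Efficacy" and 6.5 for renal impairment and dose, repeat the interval and the paired t-test within each stratum. For blood pressure and weight, SAP 5.20.1 says "For changes from the start of Nesina treatment, summary statistics and the mean 95% confidence intervals will be calculated", and 5.20.2 treats the lipids alike. Section 5.20 plans no test.

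The SAP has no site term, random effect, GEE, cluster-robust variance or sensitivity analysis by site. Site enters once, as a count in the disposition table of SAP 2.0: "number of medical site at which patients is registered".

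**The concern.** An ordinary confidence interval of a mean and a paired t-test both take the patients' changes to be mutually independent. Pairing deals with the correlation between two values from one patient. It does nothing about correlation between patients of the same site.

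Some such correlation is plausible here. Other antidiabetic drugs are unrestricted at entry (Protocol 4.1). Dietary and exercise intervention is recorded and not standardised (Protocol 9.2). Visits other than 12 and 36 months are used as labelled on the survey sheet (SAP 1.5), so their timing may follow site habit.

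At stake is whether the 95% and 5% of SAP 1.4 are the rates that the planned methods deliver. One variance choice runs through every interval and test of change in 5.20, 6.1, 6.3, 6.4 and 6.5.

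**Working it through.** **The plan's own figures.** Protocol 3.2 asks for 600 patients to identify reactions with a frequency of 0.5% at 95% confidence. This reproduces: ln(0.05)/ln(0.995) = 597.6, and the rule of three gives 3/0.005 = 600. The split of 20,000 by therapy also reproduces, as 20,000 × count/2,647. None of this bears on the HbA1c interval. The plan states no SD, power or expected width for the change, so there is no figure of that kind to reproduce.

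**Inputs.** Patients 20,000 (Protocol 3.1); sites about 1,000 (Protocol 6.0); so m = 20,000/1,000 = 20 planned registrations per site. Levels are two-sided 5% and 95% (SAP 1.4). The ICC of the change is not in the documents; 0 to 0.10 is an assumed range.

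**Formulas.** Design effect DE = 1 + (m − 1) × ICC. Correct width = planned width × √DE. Actual type I error = 2 × {1 − Φ(1.96/√DE)}. For ICC 0.05: DE = 1 + 19 × 0.05 = 1.95, √1.95 = 1.40, 1.96/1.40 = 1.40, type I error 16%.

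| ICC (assumed) | DE | Width factor | Type I error | Effective n of 20,000 | Type I error, simulated |
|---|---|---|---|---|---|
| 0 | 1.00 | 1.00 | 5% | 20,000 | 4.9% |
| 0.01 | 1.19 | 1.09 | 7% | 16,807 | 7.3% |
| 0.05 | 1.95 | 1.40 | 16% | 10,256 | 16.7% |
| 0.10 | 2.90 | 1.70 | 25% | 6,897 | 24.4% |

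The simulation drew 1,000 sites of 20 patients, 4,000 runs per ICC.

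**Other numbers per site.** The tables will not all have 20 per site:
- With 10 per site, type I error is about 6% / 10% / 16% at ICC 0.01 / 0.05 / 0.10.
- With 5 per site, it is 5.5% at ICC 0.01 and 7.4% at 0.05.
- Unequal site sizes push the other way. With an assumed coefficient of variation of 1, the effective m is 20 × (1 + 1²) = 40, and type I error is 9.6% at ICC 0.01 and 25.4% at 0.05.

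**A small stratum.** Protocol 3.2 expects 824 patients on biguanides, fewer than one per site. If they are scattered at random over 1,000 sites (assumption: Poisson), the size-weighted m is 0.824 + 1 = 1.824. At ICC 0.10, DE = 1 + 0.824 × 0.10 = 1.08 and type I error is about 6%.

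**Absolute size in the full set.** Half-width = 1.96 × SD × √(DE/20,000). With an assumed SD of change of 0.7 points, it is 0.010 at ICC 0, 0.011 at 0.01, 0.014 at 0.05 and 0.017 at 0.10. For SD 0.5 to 1.0, it runs from 0.007 to 0.014 at ICC 0 and from 0.012 to 0.024 at ICC 0.10.

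**The case against.** The strongest case on the other side is that this hardly matters. The efficacy part is largely descriptive: Protocol 10.5 has HbA1c values and changes tabulated, states no hypothesis or decision rule, and rests the sample size on adverse drug reactions. Where the design effect is largest, in the full set, the interval is so short that no clinical reading of mean HbA1c would move. Where the interval is wide, in small strata, there are few patients per site and the design effect is close to 1. This stands, and it limits the weight of the point.

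It is also fair that m = 20 describes planned registrations. The efficacy tables use a subset, "Of the Safety Analysis Set, patients who were evaluated for efficacy analysis", and only patients with values at the visit; SAP 1.5 drops discontinued patients from the 12- and 36-month values. The factors for 20 per site are therefore reference values and not a forecast for any one table, although unequal site sizes may offset part of the loss.

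Finally, a shared HbA1c scale is a weak source of correlation. SAP 1.1 converts JDS values to NGSP, and a stable laboratory offset cancels in a change from baseline. What remains is site differences in the change itself, whose size is unknown.

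These arguments reduce the consequence. They do not supply the missing allowance: SAP 1.4 still states error rates that the methods meet only if the site ICC is 0.

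**Conclusion.** The point holds in conditional form. The SAP makes no allowance for site. If the site ICC of the change is above 0, the 95% intervals in 5.20, 6.1, 6.3, 6.4 and 6.5 are too narrow, and the paired t-tests in 6.1, 6.3, 6.4 and 6.5 reject more often than 5%. The size depends on an ICC and site sizes that the documents do not give; at ICC 0 there is no error.

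A reader might infer more than this, without support in the documents:
- That the intervals are certainly too narrow. This needs an ICC above 0, which is plausible but not shown.
- That the small strata suffer most. The formula says the opposite, unless a stratum is concentrated in a few sites, and nothing shows that. The effect is largest in the full sets and large strata.
- That type I error is inflated for weight, blood pressure and lipids. Section 5.20 plans intervals only, so coverage is affected but there is no test.
- That the overall HbA1c result is in doubt. It is not, given the half-widths above.

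This is a cheap improvement to the stated error rates and to results near the boundary.

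**What to change.** In SAP 5.20, 6.1, 6.3, 6.4 and 6.5, take the interval of the mean change, and the p-value where a test is planned, from an intercept-only regression with standard errors clustered on registration site. Count a site once across its departments, as SAP 2.0 already does. Report the ICC of each change, so that the reader can see how much the clustering mattered.

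The cost is small: one option in the program and a site identifier already needed for the disposition table. Every point estimate stays the same. With about 1,000 clusters the clustered variance is reliable in the full sets, and if the ICC is 0 it returns essentially the planned interval. If the ICC is above 0, the intervals are wider, by roughly the factors in the table at 20 patients per site. In a stratum drawn from very few sites the clustered variance is itself unstable, so the number of sites should be shown beside the number of patients.
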